- g Swabs will only be analyzed (sequenced) if serum nucleocapsid protein ELISA testing and/or NAAT-based SARS-CoV-2 testing detects SARS-CoV-2 (with or without symptoms). Oral swabs for SARS-CoV-2 sequencing must be collected at the same day/time (±30 minutes) as the oral swabs for NAAT-based SARS-CoV-2 for screening/surveillance.
- h Group B transplant subjects (Cohort 13 of the BNT162-01 trial) will be followed according to this SoA; BUT they will NOT receive their second vaccination on Visit 3 and no diaries will be distributed; their second vaccination will be administered based on SRC recommendation. Thereafter Group B transplant subjects (Cohort 13 of the BNT162-01 trial) will be followed according to the SoA in Table 2a.

i Issue thermometer if not available from parent trial, for subjects to measure their body temperature each day and if they experience flu-like symptoms.

PioNTook SE	Clinical Trial Drotocol	Page 14 of 91
DIDINTECTIOE		Version: 4.0
Confidential	BNT162-14	
-		Date: 20 JAN 2022

- j Only AEs related to IMP, AESIs, SAEs, and all AEs linked to confirmed COVID-19 cases will be recorded until the end of trial. For trial subjects who receive non-trial SARS-CoV-2 vaccinations, the AEs expected to be captured after these vaccinations are within the frame of post-marketing safety data reporting (see Section 8.3.1) and should not be recorded in the CRF.
- k Only for Group B transplant subjects: only AEs related to IMP, AESIs, SAEs, and all AEs linked to confirmed COVID-19 cases will be recorded until the end of trial. For trial subjects who receive non-trial SARS-CoV-2 vaccinations, the AEs expected to be captured after these vaccinations are within the frame of post-marketing safety data reporting (see Section 8.3.1) and should not be recorded in the CRF.
- I For subjects who receive non-trial SARS-CoV-2 vaccinations there will be no sampling in subsequent visits. Information about these vaccinations may be received outside of a planned visit and can be collected remotely, e.g., by phone. In such cases information on physical examination and vital signs can be skipped. However, AEs that occurred prior to administration of non-trial vaccine must be enquired and should be recorded as stated in footnotes "j" and "k".

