Record non-trial SARS-CoV-2 vaccinations ^j		Х	х	Х	Х	х	х	Х	х

Note: The SoA allows for ad hoc SARS-CoV-2 testing for symptomatic or asymptomatic subjects.

- a Brief (symptom-directed) physical examination; no height measurement.
- b Vital signs: systolic/diastolic blood pressure, pulse rate, respiratory rate, and body temperature; body weight only at Visit 0.
- c Vital signs pre-dose on days with IMP injection.
- d Clinical laboratory tests: (Chemistry) alkaline phosphatase, creatinine, ferritin, C-reactive protein, albumin, alanine aminotransferase, amylase, aspartate aminotransferase, gamma glutamyl transpeptidase, total bilirubin, blood urea nitrogen, glucose, lipase, sodium, potassium, calcium; (Hematology) hemoglobin, hematocrit, red blood cell count, white blood cell count and differential (neutrophils, lymphocytes, monocytes, eosinophils, basophils), platelet count. Only in women who are not WOCBP (to confirm post-menopausal status): follicle stimulating hormone at Visit 0. Also to be performed if clinically indicated at any visit.
- e Oral swab for SARS-CoV-2 testing either on Day -1 or at Visit 1 on Day 1.
- f Will be tested within 24 h either at a central laboratory or a "point of care" device at the trial site or a local laboratory of the trial site.
- g Swabs will only be analyzed (sequenced) if serum nucleocapsid protein ELISA testing and/or NAAT-based SARS-CoV-2 testing detects SARS-CoV-2 (with or without symptoms). Oral swabs for SARS-CoV-2 sequencing must be collected at the same day/time (±30 minutes) as the oral swabs for NAAT-based SARS-CoV-2 for screening/surveillance.
- h Only, AESIs, SAEs, and all AEs linked to confirmed COVID-19 cases will be recorded until the end of trial. For subjects who receive non-trial SARS-CoV-2 vaccinations, the AEs expected to be captured after these vaccinations are within the frame of post-marketing safety data reporting (see Section 8.3.1).
- i For subjects who receive non-trial SARS-CoV-2 vaccinations there will be no sampling in subsequent visits. Information about these vaccinations may be received outside of a planned visit and can be collected remotely, e.g., by phone. In such cases information on physical examination and vital signs can be skipped. However, AEs that occurred prior to administration of non-trial vaccine must be enquired and should be recorded as stated in footnote "i".

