A Safety Review Committee (SRC) will be reviewing emerging safety data at least every 16 weeks until the last enrolled subject in Group A has completed 28 d of follow-up. The SRC may then decide to decrease the frequency of its cumulative safety data reviews to a minimum of once a year. The SRC will also review data from Group B (e.g., SUSARS) on an as needed basis but also specifically data emerging from the Group B transplant subjects.

For a summary of the trial as a flow diagram, see the Schema in Section 1.2. For the planned assessments and visits, see the Schedule of Activities (SoA) in Section 1.3.

This trial will enroll healthy volunteers aged ≥ 18 years who received one or two previous injections of a BNT162 candidate vaccine in either the BNT162-01 trial or the BNT162-04 trial. Volunteers will not be enrolled if they have received any COVID-19 vaccine outside of their parent trial.

The maximum number of trial subjects in the Group A (BNT162-01 trial subjects in Cohorts 1 to 14 who received 2 x Comirnaty 30 μ g) will be 90 and in Group B (all other BNT162-01 or BNT162-04 trial subjects) will be 459. A subset of Group B (n = 129) will be asked to participate in an immunologic subset evaluation.

Group A (previous 2 x Comirnaty 30 µg recipients from BNT162-01): n = 90

- BNT162-01 trial Cohorts 2 and 10: n = 24
- BNT162-01 trial Cohort 12: n = 31 (of 90)
- BNT162-01 trial Cohort 13: n = 15 HIV-infected subjects
- BNT162-01 trial Cohort 14: n = 20

BioNTech SE	Clinical Trial Protocol	Page 38 of 91 Version: 4.0
Confidential	DINT 102-14	Date: 20 JAN 2022

The immunology subset of Group B (BNT162-01 or BNT162-04 trial subjects who did not receive 2 x Comirnaty 30 μ g and Cohort 13 transplant patients) whom will be asked to participate in reactogenicity and detailed immunologic assessments: n = 129

- BNT162-01 trial BNT162b1 Cohorts 2, 5 and 1: n = 36 (of 120)
- BNT162-01 trial BNT 162b2 Cohort 11: n = 30
- BNT162-01 trial BNT 162b2 Cohort 13: n = 15 transplant subjects
- BNT162-04 trial BNT162b3 younger Cohorts 1, 2, 5, 7: n = 48 (of 96)

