The following TEAE types will be analyzed for Group A and the immunology subset of Group B:

- Any TEAE
- Related TEAE, i.e., suspected unexpected serious adverse reactions (SUSARs) which will be described in safety reports
- Any Grade ≥3 TEAE
- Any related Grade ≥3 TEAE
- Any treatment emergent serious adverse event (TESAE)
- Related TESAE
- TEAESI

- TEAEs linked to confirmed COVID-19 cases (TEAEs with preferred term = 'COVID-19')
- Deaths

The following AE types will be analyzed for all groups if applicable:

- Any AE
- Related AE
- Any Grade ≥3 AE
- Any related Grade ≥3 AE
- Any serious adverse event (SAE)
- Related SAE
- AESI
- Related AESI
- Any AEs linked to confirmed COVID-19 cases (AEs with preferred term = 'COVID-19')
- Deaths

Overall summary of TEAEs

For Group A and the immunology subset of Group B, the number and percentage of subjects reporting at least one TEAE and the number of TEAEs will be summarized for all TEAE types defined above overall.

For Group B, the number and percentage of subjects reporting at least one

- SAE
- AESIs

will be summarized.

For Group A and the immunology subset of Group B, the number and percentage of subjects reporting at least one TEAE and the number of TEAEs will be summarized by PT nested within SOC for each of the following AE types: Any TEAE, Related TEAE, Any TESAE, Related TESAE, TEAEs leading to treatment discontinuation, solicited TEAEs and fatal TEAE.

For Group B, the number and percentage of subjects reporting at least one TESAE will be summarized by PT nested within SOC.

If a SOC and PT is reported more than once for a subject, the subject will only be counted once for this SOC and PT at the worst grade level. All TEAE summary tables will be sorted alphabetically by SOC and PT within SOC.

TEAE by grade

For Group A and the immunology subset of Group B, the number and percentage of subjects with TEAEs and TESAEs will be summarized by worst grade by PT nested within SOC by time interval.

For Group B, the number and percentage of subjects with TESAEs will be summarized by worst grade by PT nested within SOC.

The worst grade will be counted if a TEAE is reported more than once by the same subject for this SOC and PT.

AEs

The number and percentage of subjects reporting at least one AE and the number of AEs will be summarized for the above defined AE types for all groups.

SAEs

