The number and percentage of subjects reporting at least one SAE and the number of SAEs will be summarized by PT nested within SOC for each of the following AE types: Any SAE, Related SAE, fatal SAE and related fatal SAE.

Non-SAEs

The number and percentage of subjects reporting at least one non-SAE and the number of non-SAEs with >5% within any arm or reporting group will be summarized by PT nested within SOC.

AE listings

All TEAEs of subjects that withdrew due to AE, SAEs, and AESIs will be listed. The duration of an AE will be calculated in hours. If for an AE the time is missing then the duration will be calculated in days.

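### SAP 6.4.3 tabulates any, related, Grade ≥3 and non-serious AEs for all of Group B, although most of Group B has only SAEs, AESIs and COVID-19-linked AEs recorded

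*SAP*

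**What the plan says.** **Collection.** Protocol 1.3 has a separate schedule for each part of the trial. Table 3 covers Group B subjects outside the immunology subset. Its footnote h applies to AE recording at every visit: "Only, AESIs, SAEs, and all AEs linked to confirmed COVID-19 cases will be recorded until the end of trial". Related AEs are not on that list. In Table 2, for the immunology subset, the corresponding footnote j applies only at Visits 6 and 7 and keeps related AEs: "Only AEs related to IMP, AESIs, SAEs, and all AEs linked to confirmed COVID-19 cases will be recorded until the end of trial". Table 1 (Group A) brings in a similar limit from Visit 5.

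**Numbers.** Protocol 4.1 gives maxima: "in Group B (all other BNT162-01 or BNT162-04 trial subjects) will be 459", and "A subset of Group B (n = 129) will be asked to participate in an immunologic subset evaluation". All transplant subjects are in that subset: "BNT162-01 trial BNT 162b2 Cohort 13: n = 15 transplant subjects".

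**Analysis.** SAP 6.4.3 has a list of AE types headed "The following AE types will be analyzed for all groups if applicable". It contains any AE, related AE, Grade ≥3 AE, related Grade ≥3 AE, SAE, related SAE, AESI, related AESI, COVID-19 AE and deaths. The paragraph headed AEs then has subject counts and percentages "summarized for the above defined AE types for all groups". The paragraph headed Non-SAEs plans a table by system organ class and preferred term, covering "the number of non-SAEs with >5% within any arm or reporting group", and names no group.

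**Layout and denominator.** SAP 6.1.1 gives Group B by transplant status and in total, and separately the immunology subset by transplant status and in total. Percentages use the analysis-set N unless stated otherwise. For AEs that set is the Safety Set. No other denominator is stated for the tables above.

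**The concern.** The tables combine two parts of Group B that are observed under different rules. In the larger part, a non-serious event that is neither an AESI nor linked to COVID-19 cannot enter the database, yet those subjects count in the denominator. The column total then reflects the recording rule as well as tolerability.

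Related AE is hit most directly: outside the subset, a vaccine-related event is recorded only if it is also serious, an AESI or COVID-19-linked. The same tables show Group A, where all AEs are recorded early in follow-up. No footnote on the difference is planned, so a reader could take a lower Group B percentage as better tolerability of the two-dose regimen.

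**Working it through.** **1. Counts (Protocol 4.1).** The listed subset cohorts add to 36 + 30 + 15 + 48 = 129, which reproduces the stated subset size.

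- Restricted recording: 459 − 129 = 330, and 330/459 = 71.9%.
- Non-transplant column: 459 − 15 = 444 subjects, of whom 129 − 15 = 114 are in the subset. Restricted: 330/444 = 74.3%.
- Transplant column: 15 subjects, all in the subset, none restricted by Table 3.

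**2. What each column records (Protocol 1.3).**

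| Column | AE recording |
|---|---|
| Group A (Table 1) | All AEs at Visits 1, 2 and 4; limited from Visit 5 |
| Immunology subset, non-transplant (Table 2) | No limit before Visit 6 |
| Immunology subset, transplant (Tables 2 and 2a) | No limit before Visit 5; unlimited again at Visits 8 to 10 around injection 2 |
| Rest of Group B (Table 3) | SAEs, AESIs and COVID-19-linked AEs only, at every visit |

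All AEs are thus recorded through Visit 4 in Group A and the subset, and at no visit in the other 330.

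**3. Formula.** Let p be the proportion with the event under the subset's collection, and q the proportion of the 330 with a recordable event. Assume the same underlying risk in both parts of Group B.

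- Group B total = (129p + 330q)/459
- Group B non-transplant = (114p + 330q)/444
- Total relative to p = 0.281 + 0.719 × (q/p)

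Recordable events are a subset of all AEs, so q cannot exceed p under this assumption, and the bias is downward.

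**4. Results.** The documents give neither p nor q. With p = 40% assumed:

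| q (assumed) | Group B total | Group B non-transplant |
|---|---|---|
| 2% | (51.6 + 6.6)/459 = 12.7% | (45.6 + 6.6)/444 = 11.8% |
| 5% | (51.6 + 16.5)/459 = 14.8% | (45.6 + 16.5)/444 = 14.0% |
| 10% | (51.6 + 33.0)/459 = 18.4% | (45.6 + 33.0)/444 = 17.7% |
| 20% | (51.6 + 66.0)/459 = 25.6% | (45.6 + 66.0)/444 = 25.1% |

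With p = 40%, the shortfall in the total runs from about 3.2-fold (40/12.7) to 1.6-fold (40/25.6). For an event type that is never serious, an AESI or COVID-19-linked, q = 0 and the total shows 28.1% of p whatever p is (25.7% in the non-transplant column).

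**5. Rows affected.** Any AE, related AE and non-SAE are diluted. Grade ≥3 and related Grade ≥3 are diluted less, because severe events that are also serious are recorded in everyone. SAE, related SAE, AESI, related AESI, COVID-19 AE and deaths are collected in all of Group B and are not diluted.

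**The case against.** The best defence is the qualifier *if applicable*. The later paragraph refers back to the list it qualifies, so it may inherit the condition, and a programmer could read it as limiting each AE type to subjects in whom it is collected. The surrounding text supports that intent. SAP 6.4.3 limits TEAE summaries to Group A and the immunology subset and names only SAEs and AESIs in the overall summary for Group B. Protocol 9.4.2 likewise plans AESIs and SAEs for Group B. This shows the wording may be unintended, but it does not settle the matter. The qualifier is undefined, and events of every listed type can occur in Group B through SAEs, AESIs and COVID-19 cases, so the columns would fill. The Non-SAEs paragraph has no qualifier at all. Protocol 8.3.1 speaks of recording all AEs, but at the time points in the schedule, so the Table 3 footnote still governs.

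It is also fair that the harm is bounded. Nothing is tested, Group B is not randomised, no comparison of Group A with Group B is planned, and the immunology subset has its own columns.

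Four stronger readings are tempting, and the documents do not support them:

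- **Group A and the subset have complete AE capture throughout.** They do not; Tables 1, 2 and 2a limit recording at later visits.
- **The 5% cut would hide terms diluted in the Group B total.** The rule is met by any arm or reporting group, and the immunology subset is a reporting group, so a common term there can trigger display.
- **The primary safety results are biased.** SAEs and AESIs are collected in everyone, and reactogenicity and unsolicited TEAEs are confined to Group A and the subset.
- **The SAP departs from the protocol without permission.** Protocol 9.4.2 allows further AE analyses in the SAP. The issue is interpretability.

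**Conclusion.** The point holds for the Group B total and non-transplant columns of the any, related, Grade ≥3, related Grade ≥3 and non-SAE tables. Followed as written, these percentages are biased low by the collection rule. They cannot be compared with Group A or the immunology subset.

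The direction follows from the documents, given similar underlying risk in the two parts of Group B. The size does not: the 40% and the 2% to 20% are assumptions, and the 330 of 459 and 330 of 444 are planned maxima that actual enrolment may change. COVID-19-linked AEs are recorded in all subjects, so q need not be small and a severalfold shortfall should not be presumed.

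The immunology-subset and transplant columns and the primary endpoints stand. This should be corrected before the tables are produced, but it does not threaten the main safety conclusions.

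**What to change.** In SAP 6.4.3:

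- Limit the any AE, related AE, Grade ≥3 AE, related Grade ≥3 AE and non-SAE tables to Group A and the Group B immunology subset.
- For Group B overall, show only SAE, related SAE, AESI, related AESI, COVID-19-linked AE and deaths.
- Footnote each column with the AE types recorded and the visits at which recording was unrestricted, since Group A and the subset also change rule during follow-up.
- Delete or define the applicability qualifier.

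This is a short text edit. It needs no new data, yields fewer tables, and matches Protocol 9.4.2 and the SAP's own limit on TEAE tables. A footnote alone would warn readers but would leave percentages that estimate no useful quantity.

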b Vital signs: systolic/diastolic blood pressure, pulse rate, respiratory rate, and body temperature; body weight only at Visit 0.

c Vital signs pre-dose and at 1 h (±15 minutes) on days with IMP injection.

d Dipstick urine analysis: glucose, bilirubin, ketone, specific gravity, blood, pH, protein, urobilinogen, nitrite, and leukocytes. Microscopic urinalysis: if warranted by dipstick results, urine sediment will be microscopically examined for the presence of red blood cells, white blood cells, casts, crystals, epithelial cells, and bacteria.

e Clinical laboratory tests: (Chemistry) alkaline phosphatase, creatinine, ferritin, C-reactive protein, albumin, alanine aminotransferase, amylase, aspartate aminotransferase, gamma glutamyl transpeptidase, total bilirubin, blood urea nitrogen, glucose, lipase, sodium, potassium, calcium; (Hematology) hemoglobin, hematocrit, red blood cell count, white blood cell count and differential (neutrophils, lymphocytes, monocytes, eosinophils, basophils), platelet count. Only in women who are not WOCBP (to confirm post-menopausal status): follicle stimulating hormone at Visit 0.

f Will be tested within 24 h, either at a central laboratory or a "point of care" device at the trial site or a local laboratory of the trial site.

g Oral swab for SARS-CoV-2 testing either on Day -1 or at Visit 1 on Day 1.

h Swabs will only be analyzed (sequenced) if serum nucleocapsid protein ELISA testing and/or NAAT-based SARS-CoV-2 testing detects SARS-CoV-2 (with or without symptoms). Oral swabs for SARS-CoV-2 sequencing must be collected at the same day/time (±30 minutes) as the oral swabs for NAAT-based SARS-CoV-2 for screening/surveillance.

BioNTech SE	
Confidential	

Clinical Trial Protocol BNT162-14 Page 11 of 91 Version: 4.0 Date: 20 JAN 2022

- i Only AEs related to IMP, AESIs, and SAEs. All AEs linked to confirmed COVID-19 cases will be recorded. For trial subjects who receive non-trial SARS-CoV-2 vaccinations, the AEs expected to be captured after these vaccinations are within the frame of post-marketing safety data reporting (see Section 8.3.1) and should not be recorded in the CRF.
- j Issue thermometer if not available from parent trial, for subjects to measure their body temperature each day and if they experience flu-like symptoms.

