10.3.1.9 Documentation of particular situations

AEs that are secondary to other events:

In general, AEs that are secondary to other events (e.g., cascade events or clinical sequelae) should be identified by their primary cause, with the exception of severe or serious secondary events. A medically significant secondary AE that is separated in time from the initiating event should be documented as an independent AE in source data and CRF. For example:

- If vomiting results in mild dehydration with no additional treatment in a healthy adult, only vomiting should be documented as AE.
- If vomiting results in severe dehydration, both events should be documented as AEs separately.

Abnormal clinical laboratory results and vital signs values:

Not every laboratory or vital signs abnormality needs to be documented as AE. For clinically significant laboratory/vital signs abnormalities the following definitions and documentation rules apply:

- If a laboratory/vital signs abnormality is a sign of a disease or syndrome, the laboratory/vital signs abnormality is clinically significant and only the diagnosis of the causing disease or syndrome needs to be documented as AE.
- If a clinical laboratory/vital signs abnormality results in specific symptoms but no diagnosis of a disease or syndrome can be made, the laboratory/vital signs abnormality is clinically significant and only the symptoms need to be documented as AEs.
- If a clinical laboratory/vital signs abnormality is not a sign of a disease or syndrome and does not result in specific symptoms but leads to a change in trial treatment or in a medical intervention, the laboratory/vital signs abnormality is clinically significant and must be documented as AE.
- If a clinical laboratory/vital signs abnormality is not considered clinically significant by the investigator, then an AE does not need to be documented.

AEs associated with an overdose or error in drug administration:

- An overdose or incorrect administration of a drug is not itself an AE, but it may result in an AE. For a definition of an overdose, see Section 8.4.
- All AEs associated with an overdose or incorrect administration should be documented as AE in source data and CRF and reported as SAE if applicable.

AEs of proven COVID-19 disease:

Any case of proven COVID-19 disease occurring until the last FU visit should be reported as an SAE/AE.

BioNTech SE	
Confidential	

Page 72 of 91 Version: 4.0 Date: 20 JAN 2022

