6.4.3. Adverse events

Definition

For detailed information on adverse events see Section 10.3 of the protocol. Solicited AEs that are recorded from the subject diaries on the reactogenicity CRFs will not be reported as AEs unless the solicited AE meets criteria for SAE or begins after Day 8 or started before Day 8 and continues past Day 8.

Adverse events (AEs) will be coded using the Version MedDRA[®] 24.0 to get a system organ class (SOC) and preferred term (PT) for each AE.

A TEAE is defined as any AE with an onset after the first injection (Dose 1) (if the AE was absent before the first injection) or worsened after the first injection (Dose 1) (if the AE was present before the first injection (Dose 1)). AEs with an onset date more than 28 days after the last injection will be considered as treatment emergent only if

assessed as related to IMP by the investigator. AEs that cannot be determined to not be treatment emergent due to missing date or time will be defined as TEAE.

Note: To clarify the definition in the protocol, AEs with an onset date at the date of the first injection (Dose 1) will only be considered as treatment emergent if the AE occurred after the first injection (Dose 1). AEs with missing time and occurring on the day of Dose 1 or AEs with missing date will be analyzed as treatment emergent.

TEAEs will be evaluated for following time interval and groups:

- Up to 28 days after the first IMP injection (Group A and immunology subset of Group B)
- After the first IMP injection up to 28 days after the second IMP injection (immunology subset of Group B non-transplant)
- After the second IMP up to 28 days after the second IMP injection (immunology subset of Group B transplant)
- All TEAEs (Group A and immunology subset of Group B)

AEs are assigned to the time interval according to their start date and time. AEs with missing date will be assigned to each of the respective intervals if it cannot be ruled out, that it belongs to the time interval.

Adverse events of special interest (AESIs)

The following events will be reported as AESIs: myocarditis, pericarditis, anaphylaxis, thromboembolic events (e.g., deep vein thrombosis, stroke, myocardial infarction), immune thrombocytopenia and immune based neurologic events (e.g., optic neuropathy, Guillain-Barré syndrome). AESIs are recorded in the CRF.

AESIs and SAEs will be evaluated up to 26 weeks after the ICF was signed for all groups.

Analysis

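### SAP 6.4.3 defines COVID-19-linked AEs by the single preferred term COVID-19, so separately recorded complications drop out of the linked-event count and lose their attribution

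*SAP*

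**What the plan says.** The SAP uses the same rule twice in Section 6.4.3. For Group A and the Group B immunology subset it is "TEAEs linked to confirmed COVID-19 cases (TEAEs with preferred term = 'COVID-19". For all groups it is "Any AEs linked to confirmed COVID-19 cases (AEs with preferred term = 'COVID-19". Section 6.4.3 also has the dictionary assign a "preferred term (PT) for each AE". It provides no link flag, term list, standardised query or time window that would bring other terms into the category. SAP Appendix 1 (Section 7.1) lists one departure from the protocol, on AE grade, and it is unrelated to this point.

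The protocol's class is wider. Footnote i to Table 1 in Section 1.3 (Group A) reads "All AEs linked to confirmed COVID-19 cases will be recorded", and the footnotes to Tables 2 and 2a say the same in substance. For Group B outside the immunology subset, footnote h to Table 3 makes these events one of only three classes collected: "Only, AESIs, SAEs, and all AEs linked to confirmed COVID-19 cases will be recorded until the end of trial".

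Protocol 10.3.1.9 says how secondary events are to be recorded. They "should be identified by their primary cause, with the exception of severe or serious secondary events". It adds: "A medically significant secondary AE that is separated in time from the initiating event should be documented as an independent AE". Its worked example produces two records: "If vomiting results in severe dehydration, both events should be documented as AEs separately".

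**The concern.** The label and the selection rule describe different sets of events. The label promises all AEs linked to a confirmed case. The rule returns only the record carrying the diagnosis. Where sites follow 10.3.1.9, the records left out are the complications judged severe, serious, or medically significant and separated in time from the diagnosis.

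This is the only AE category that the SAP gives to COVID-19. A reader of the report would take its event count as the number of COVID-19-linked events and would have no sign that complications sit elsewhere under other terms. At stake is a correct description of what happened to subjects who became infected, in a trial that collects those events on purpose.

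**Working it through.** No figure in the plan relates to this point, and no hypothesis is tested (protocol 9.1, SAP 2). The check is therefore a comparison of rules.

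**Step 1. Count under each rule.** Take one confirmed case whose diagnosis is coded to COVID-19, with k complications recorded separately under other terms.

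- Protocol class: 1 + k linked events.
- SAP row: 1 event.
- Events omitted: k, a share of k/(1 + k). As an illustration only, k = 0, 1, 2, 3 gives shares of 0, 1/2, 2/3 and 3/4.
- Subjects counted: 1 under both rules.

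If the diagnosis itself were coded to another term, the SAP row would count 0 subjects instead of 1. Neither k nor the number of cases is in the documents.

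**Step 2. Where the omitted events can still be seen (SAP 6.4.3).**

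| Complication | Still shown in | Link to COVID-19 shown? |
|---|---|---|
| Serious | SAE tables by term within system organ class; SAE listing; deaths if fatal | No |
| On the AESI list | AESI counts and listing | No |
| Severe, non-serious, treatment-emergent (Group A, immunology subset) | TEAE tables by term and grade | No |
| Severe, non-serious, not treatment-emergent | Overall Grade ≥3 AE count; non-serious table by term only above its 5% threshold | No |

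**Step 3. The last row.** An AE starting more than 28 days after the last injection is treatment-emergent only if the investigator judges it related to the vaccine. A later complication of COVID-19 judged unrelated therefore leaves the TEAE tables. The remaining table by term for non-serious events shows only those above 5% in some arm or reporting group. Reading the threshold as a share of subjects and using planned maximum sizes (Group A of 90 split 2:1 gives 60 and 30), the fewest subjects needed are:

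- Group B total, n = 459: 0.05 × 459 = 22.95, so 23.
- Group B immunology subset, n = 129: 6.45, so 7.
- Group A BNT162b2s01 arm, n = 60: 3.0, so 4.
- Group A Comirnaty arm, n = 30: 1.5, so 2.
- Transplant subjects, n = 15: 0.75, so 1.

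A single event would thus show in the transplant group (1/15 = 6.7%) but not in either Group A arm or in Group B as a whole. The AE listings named in 6.4.3 cover TEAEs of subjects who withdrew because of an AE, SAEs and AESIs, so they do not reliably include such an event.

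**Step 4. Primary endpoints.** The SAE and AESI proportions are selected by seriousness and by the AESI list. COVID-19 is not on the current AESI list (protocol 8.3.8). Neither proportion depends on this row.

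**The case against.** The strongest reply is that this is a labelling matter in a descriptive row that belongs to no endpoint. Several parts of it stand.

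- The protocol's Notes for the reader treat 'should' as a recommendation. Section 10.3.1.7 also asks that AEs belonging to one clinical event be placed under that event. How many complications receive their own record depends on the site and may be small.
- The events remain in the data and mostly in other tables. SARS-CoV-2 results are listed (SAP 6.8.4) and important CRF data are listed by subject (SAP 6.1.1), so a patient reader could match some cases by hand.
- In Group B outside the immunology subset (at most 459 − 129 = 330 subjects), a recorded AE that is neither an SAE nor an AESI is COVID-19-linked by the collection rule itself.
- Protocol 9.4.2 plans no analysis of this class, so it can be argued whether Appendix 1 had to declare the narrowing.

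None of this makes the row match its label, and none supplies the link in aggregate.

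A reader might infer more: that complications vanish from the analysis, or that the row understates COVID-19 severity and hides a possible worsening by the vaccines, which protocol 2.3.1 says has not been seen but cannot be excluded. The documents do not support this. The row reports subjects and event counts, not grade. The diagnosis record carries its own grade and seriousness. No objective concerns COVID-19 severity. Every treated subject receives a BNT162 vaccine, so no version of this row could show that vaccination worsens later illness.

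**Conclusion.** The definition is narrower than the class the protocol collects and than the SAP's own label. Followed as written, it undercounts COVID-19-linked events by the number of complications recorded under other terms and removes their attribution to COVID-19. The loss is clearest for severe, non-serious events that start more than 28 days after the last injection and are judged unrelated to the vaccine. The size in events cannot be given, because the documents contain no case or complication counts.

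The conclusion assumes that sites follow the recommendation in 10.3.1.9 at least sometimes and that separate records are coded to terms other than COVID-19. The subject count is right provided each case is coded to COVID-19. This is a modest error in a stated rule, worth correcting before the tables are produced, and it does not touch the primary results.

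**What to change.** In SAP 6.4.3, define the category as AEs that the investigator links to a confirmed SARS-CoV-2 case, whatever the preferred term. If the CRF holds no such link (the CRF is not among the documents), identify the events by medical review of AE records against SARS-CoV-2 test results, including outside positives obtained under protocol 8.2.7. A bare time window around a positive test is not enough, because it would take in coincidental AEs, including those in asymptomatic subjects found at surveillance visits.

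Report the number of subjects, number of events, worst grade and seriousness. Keep the single-term count as its own row, labelled as AEs with preferred term COVID-19. State the definition and its relation to the protocol class in Appendix 1.

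The cost is a change of SAP wording, a match of AE records to test results already collected, and a small medical review. Linkage needs some judgement, but sites already make it when they decide which late AEs to record under the Section 1.3 footnotes.
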